2.4 Treatments (study treatment, rescue medication and concomitant therapies)

The safety set will be used for all analyses associated with study treatment and other medications/non-drug therapy.

2.4.1 Study treatment

The duration of exposure (weeks), cumulative dose, actual dose intensity and relative dose intensity will be listed and summarized for the study drugs PDR001 and LAG525 based on safety set by means of descriptive statistics. Categories for relative dose intensity of PDR001 and LAG525 will be specified as $\leq 75\%$, $>75\% - \leq 90\%$, $> 90\% - \leq 110\%$ and $> 110\%$; the number and proportion of patients within each category will be presented.

In addition, dose interruptions and dose permanently discontinued (including the reasons for these) will be listed and summarized. All dosage administration records will be listed.

Duration of exposure to study treatment

Duration of exposure to study treatment is calculated as follows:

Duration of exposure to study drug (days) = (last date of exposure to study drug) – (date of first administration of study drug) + 1.

Duration of exposure (weeks) = (Duration of exposure, days) / 7.

The last date of exposure to PDR001 Q3W is the planned end date of the last cycle in which the last non-zero dose of PDR001 was last administered (i.e last date of administration + 20 day)).

Similarly, the last date of exposure to LAG525 Q3W is defined as the last date of LAG525 administration + 20 days.

The last date of exposure for the combination PDR001+LAG525 is the last date of exposure to PDR001 or LAG525 (defined as above), whichever is later.

Note: If the patient died or was lost to follow-up before the derived last date, the last date of exposure to investigational drug/study treatment is the date of death or the date of last contact, respectively.

Summary of duration of exposure of study drug in appropriate time units will include categorical summaries (<6, 6-<12, 12-<18, 18-<24 and ≥ 24 weeks) and continuous summaries (i.e. mean, standard deviation etc) in weeks. The duration of exposure to study drug may include periods of temporary interruption (zerodose periods).

Actual cumulative dose

Actual cumulative dose is defined as the total dose administered over the duration for which the subject is on the study treatment as documented in the Dose Administration eCRF, and will be summarized for each of the study treatment components separately.

For patients who did not take any drug the cumulative dose is by definition equal to zero.

- Actual dose (mg) = Sum of (actual dose per an infusion) for all infusions.

Dose intensity and relative dose intensity

The dose intensity(DI), expressed as mg/*unit of time*, and the relative dose intensity(RDI) are defined as follows:

- Dose intensity (mg/ *unit of time*) = (Actual cumulative dose, mg) / (Duration of exposure, *unit of time*).
- Relative dose intensity(%) = (Dose intensity, mg/*unit of time*) / (Planned dose intensity, mg/*unit of time*)*100.

Planned dose intensity (mg/*unit of time*) can be calculated as follows:

- Planned dose intensity (mg/unit of time) = (Planned cumulative dose, mg) / (Duration of exposure,*unit of time*)
- Planned cumulative dose (mg) = Sum of (dose prescribed, mg) for all infusions

Dose interruptions and permanent discontinuations

The number of subjects who have dose interruptions, permanent discontinuations, and the reasons, will be summarized separately for each of the study treatment components.

‘Dose permanently discontinued’ from the Dosage Administration CRF pages (DAR) will be used to determine the permanent discontinuations, and Dose interruption is defined as any dose interruption flagged in the Dosage Administration CRF pages (DAR), satisfying the following criteria:

- a reason other than ‘As per protocol’,
- occurs between the first and last non-zero doses,
- follows a non-zero actual dose.

The corresponding fields ‘Reason for dose interrupted’, ‘Reason for permanent discontinuation’ will be used to summarize the reasons. Dose reductions are not permitted for PDR001 and LAG525.

Additionally, treatment beyond RECIST progression will be summarized based on safety set.

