2.6 Risks and benefits

Appropriate eligibility criteria, as well as specific dose delays and stopping rules are included in this protocol. Recommended guidelines for prophylactic or supportive management of study-drug induced adverse events are provided in [Section 6](#). The risk to subjects in this trial may be minimized by compliance with the eligibility criteria and study procedures, close clinical monitoring, and stopping rules.

Infusion of drugs such as PDR001 and /or LAG525 can be associated with reactions especially during the first exposure. Infusion reactions usually consist of symptoms such as fever, chills, nausea, vomiting, headache, dizziness, dyspnea, hypotension, rash, and asthenia.

PDR001: The most frequent side effects caused by single-agent PDR001 include: diarrhea, nausea, vomiting, constipation, gastritis, hypothyroidism, hyperthyroidism, itchiness, skin reactions (such as rash, dryness, redness, hives), low red blood cell count, dry mouth, inflammation in the mouth, canker sores, loss of appetite, decreased blood sodium, increased blood sugar, pain in joints, muscles, nerves & skin, swelling in the face or limbs, pneumonia, abnormal liver function tests, increased lipase, decreased lymphocytes, weight loss, fever, chills, malaise, weakness, fatigue, abdominal discomfort and pain, shortness of breath during exercise or at rest, cough, vertigo/dizziness, and headache.

Less frequent side effects caused by single agent PDR001 include the following severe immune reactions: colitis requiring hospitalization; pneumonitis & pneumonia, hepatitis with abnormal liver test results; and polymyositis with muscle weakness,

LAG525: The most frequent side effects caused by single-agent LAG525 include: fatigue, nausea, vomiting, fever, abnormal liver function tests, loss of appetite, joint and muscle pain, itchiness, skin reactions such as rash, dryness, redness & hives, hypothyroidism, increased amylase, increased lipase, hyperkalemia, hyperuricemia, constipation, dry mouth, lack of energy, abdominal pain, diarrhea, and weight loss.

One case of acute kidney injury possibly related to LAG525 occurred in the setting of widespread metastatic disease, tumor lysis syndrome, and multiple organ failure leading to death. Kidney function is evaluated in all patients regularly throughout this study.

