6.3 Dose modifications

6.3.1 Dose modification and dose delay

Dose reductions are not permitted. PDR001 and LAG525 may be delayed due to toxicities. The dosing regimen may resume once the adverse event has resolved to grade 1 or baseline, and the start of the cycle will be shifted accordingly.

If the Investigator considers it to be in the patient's best interest to resume therapy before the toxicity has resolved to Grade 1 this may be permitted, following documented discussion with the Novartis medical monitor.

Overall, irAEs that do not recover to \leq Grade 1 or baseline at a dose of immunosuppression of ≤ 10 mg/day prednisone or equivalent (or as indicated in the [Table 6-2](#)) within 12 weeks after initiation of immunosuppressive therapy, PDR001 and LAG525 must be permanently discontinued. All interruptions or changes to study drug administration must be recorded on the Dose Administration Record eCRF.

If PDR001 and LAG525 treatment is interrupted for more than 12 weeks due to study treatment-related toxicities, then the study treatment should be permanently discontinued. If a patient who misses more than 12 weeks of study treatment has objective evidence of response (e.g. serum, urine, or marrow evidence of response that does not meet criteria for PR, or documented improvement in a physical exam finding), and in the opinion of the investigator it is in the patient's best interest to remain on study, then the patient may continue study treatment following documented approval from Novartis. Details are provided in [Table 6-2](#) below.

Table 6-2 Maximum permitted missed doses prior to permanent discontinuation of study treatment

Study drug	Maximum permitted missed consecutive doses prior to permanent discontinuation of study treatment
------------	--

PDR001	3
LAG525	3

Patients who discontinue the study for a study related AE or a study-related abnormal laboratory value must be followed as described in [Section 6.3.2](#). All interruptions or change to study drug administration must be recorded on the Dose Administration Record eCRF.

Dose delays for adverse events related to the study medication are summarized in [Appendix 5](#). Generally, following resolution of the adverse event to Grade 1 or to the patient's baseline value, the patient may resume study treatment on the same dosing schedule, if there is no evidence of disease progression.

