1.2 Study objectives and endpoints

Objectives and related endpoints are described in [Table 1-2](#) below.

For patients with solid tumors the assessment criteria will be RECIST 1.1

For patients with lymphoma, the assessment will be based on Revised Response Criteria for Malignant Lymphoma (Cheson et al 2007).

Table 1-2 Objective and related endpoints

Objective	Endpoints
Primary 
To assess clinical benefit rate (CBR) at 24 weeks of PDR001+LAG525 by tumor type in multiple solid malignancies and lymphoma.	
The primary endpoint is CBR after 24 weeks of treatment with PDR001+LAG525 based on local investigator assessment.
Secondary 
To assess overall response rate (ORR) in solid tumors and in lymphoma.To assess Time to response (TTR), Duration of response (DOR), Time to progression (TTP) and Progression free survival (PFS) rate at 1 and 2 yearsTo assess Safety and Tolerability	
Endpoint is ORR evaluated based on the PR and CR, based on local investigator assessment.Endpoints are TTR, DOR, TTP and PFS rate at 1 and 2 yearsSafety incidence and severity of adverse events (AEs) and serious adverse events (SAEs) including changes in laboratory parameters, vital signs and ECG. 
Tolerability: Dose interruptions, reductions and dose intensity

2 Statistical methods

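### Toxicity holds with no later dose are left out of the dose-interruption summary, and dose intensity does not register them

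*SAP*

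**What the plan says.** SAP Table 1-2 names the tolerability endpoint as "Tolerability: Dose interruptions, reductions and dose intensity". SAP 2.4.1 sets the unit of the summary: "The number of subjects who have dose interruptions, permanent discontinuations, and the reasons, will be summarized separately for each of the study treatment components".

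An interruption flagged on the dosing page counts only if it meets three conditions:

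- it has "a reason other than ‘As per protocol";
- it "occurs between the first and last non-zero doses";
- it "follows a non-zero actual dose".

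Permanent discontinuation comes from a separate field on the same page, which "will be used to determine the permanent discontinuations", with its own reason. Dose reductions are not permitted, so interruptions and dose intensity carry the endpoint. Exposure to each drug ends 20 days after its last non-zero dose, or at death or last contact if earlier.

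Protocol 10.3.1 (Study medication) promises the number of patients with dose changes or interruptions, with reasons, and does not require that dosing resumed. SAP section 4 lists only the two analysis-set definitions as changed from the protocol.

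Protocol 6.3.1 generally calls for permanent discontinuation once treatment "is interrupted for more than 12 weeks due to study treatment-related toxicities", so a hold can be long.

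**The concern.** The second condition makes a later dose part of the definition of an interruption. Take a patient held for toxicity who progresses, dies or withdraws before the next dose. That patient has no interruption on record, and the permanent discontinuation may be attributed to progression, death or withdrawal. The toxicity that stopped dosing then appears in neither dosing-page count.

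The rule can only lower the interruption count. The loss is likely to be greatest where progression comes soonest, so the figures for short-PFS cohorts would be affected most. A reader who sees few interruptions and full dose intensity would not know that some patients never restarted after a toxicity hold.

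Two neighbouring details are open. The SAP does not say how a flagged pause within an infusion is classified, although Protocol 2.6 warns that infusions "can be associated with reactions especially during the first exposure". It also does not define the *As per protocol* reason code, although the protocol itself requires holds for many toxicities.

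**Working it through.** **No figure to reproduce.** The documents give no interruption rate and no hold lengths. The check applies the SAP rule to invented dosing histories, then uses the plan's PFS medians for scale.

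**1. The counting rule.** Each history uses a unit dose every 21 days. The word 'between' was read as excluding or including the first and last dose dates, and 'follows' as needing an earlier dosing record or as satisfied by a part-dose in the same record. That gives four readings.

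| History | Counted as an interruption? |
|---|---|
| A. Doses days 1 and 22, held day 43, dosed day 64 | Yes, all 4 readings |
| B. Doses days 1 and 22, held days 43 and 64, then progression or death | No, all 4 |
| C. Dose day 1, held day 22, then progression | No, all 4 |
| D. First infusion paused and completed, dosing continues | Yes in 1 of 4 |
| E. Second of three infusions paused and completed | Yes, all 4 |
| F. Last infusion paused and completed | Yes in 2 of 4 (only if 'between' is inclusive) |
| G. Resumed hold coded *As per protocol* | No, all 4 |

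B and C carry the point: no reading rescues a hold without a later dose.

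**2. Dose intensity**, in doses per 3 weeks, with exposure ending at last dose + 20 days:

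- A: exposure 64 + 20 = 84 days = 4 cycles; 3/4 = 0.75. The resumed hold shows.
- B: exposure 22 + 20 = 42 days = 2 cycles; 2/2 = 1.00. With the hold included (64 + 20 = 84 days), 2/4 = 0.50.
- C: exposure 1 + 20 = 21 days; 1/1 = 1.00. With the hold included (22 + 20 = 42 days), 1/2 = 0.50.

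Relative dose intensity divides actual and planned cumulative dose by the same duration, so time cancels and it equals actual over prescribed dose summed across infusions. A held dose that generates no infusion leaves it at 100%. The SAP does not say whether a held dose enters the prescribed total.

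**3. Scale.** Inputs are the median PFS values in Protocol Table 10-1 (also SAP Table 2-1), the exponential assumption in Protocol Appendix 4, section 6.1.2, and the SAP 2.1.1.9 month of 30.3475 days.

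Check on the input: 2^(−6/median) gives 6.25, 25.00, 35.36, 43.53 and 51.13%, against stated historical rates of 6.25, 25.00, 35.40, 43.50 and 51.10%.

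Chance of a PFS event during a hold of h months = 1 − 2^(−h/median). For 12 weeks, h = 84/30.3475 = 2.77 months.

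| Cohort (median, months) | 3 weeks | 6 weeks | 12 weeks |
|---|---|---|---|
| SCLC (1.5) | 27.4% | 47.2% | 72.2% |
| Ovarian, DLBCL (3) | 14.8% | 27.4% | 47.2% |
| Prostate (4) | 11.3% | 21.3% | 38.1% |
| Gastroesophageal, NET (5) | 9.1% | 17.5% | 31.9% |
| Sarcoma (6.2) | 7.4% | 14.3% | 26.6% |

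**The case against.** The strongest reply is that this is a classification choice and other outputs cover it. The SAP separates temporary interruption from permanent discontinuation, and asking for a later dose keeps the two apart. Protocol 10.3.1 does not define interruption, so nothing in it is contradicted.

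The adverse-event tables in SAP 2.8.1 include events that led to dose adjustment or interruption, without the dosing-page conditions. Protocol 8.1.1 records the action taken for each event. An event that causes the first missed dose should have begun by the day that dose was due: 21 days after the last dose, or 25 with the 4-day visit window. That lies inside the 30-day on-treatment period of SAP 2.1.1.8. All dosing records are also listed.

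Most of this stands. A reader might infer that these holds disappear from every tolerability output; the documents do not support that. What remains is that the dosing-page summary, which is the named measure, omits them without saying so, and that neither adverse-event tables nor listings show how many holds were never followed by another dose.

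Three other inferences go too far:

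- **First-infusion pauses are certainly excluded.** This depends on how 'between' and 'follows' are read, and on whether such a pause is flagged at all. The handling is undefined.
- **The *As per protocol* code can only hide holds that the toxicity or concomitant-drug rules require.** That would need the code list or completion guidance, which the documents do not contain.
- **The percentages are the share of interruptions missed.** SAP 2.4.1 counts subjects, so one earlier resumed hold is enough to be counted. Twelve weeks is a ceiling, not a typical hold. Scheduled scans start at week 12 and then run every 6, later every 12, weeks (Protocol 4.1), so many short holds contain none. Treatment beyond progression is allowed (Protocol 7.1.4 and 7.2.1.1).

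**Conclusion.** The point holds for holds with no later dose. Under every reading of SAP 2.4.1 they are outside the interruption count; dose intensity stays at 1.00 in the two invented cases, against 0.50 with hold time included; and the discontinuation reason may record only what happened later. The bias has one direction.

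The number of subjects affected cannot be derived. The range of 27% to 72% for a 12-week hold assumes historical exponential PFS, an event acted on when it occurs, and no dosing after progression. It bounds from above the share of such holds lost through progression or death; it does not cover withdrawals, and on-study PFS may differ.

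The consequence is limited. The summary is descriptive, no tolerability test between cohorts is planned, and nothing here feeds the clinical benefit rate or the futility, expansion and success rules. It is worth correcting because the measure is a named secondary endpoint and the correction is cheap.

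**What to change.** In SAP 2.4.1:

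1. Keep the present count, labelled as resumed (temporary) interruptions.
2. Add, per component and tumor cohort, the number of subjects interrupted and not resumed, defined as a flagged interruption after the last non-zero dose of that component. Tabulate it by interruption reason and by final discontinuation reason.
3. Give the total of subjects with any interruption with and without that line.
4. Show flagged interruptions coded *As per protocol* in a separate row instead of dropping them.
5. State that a flagged within-infusion interruption, including at the first infusion, counts as an interruption.

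The dosing-page fields needed are already named in SAP 2.4.1, so no new data are required. The SAP history already records changes after database lock, so this can be a labelled additional table. The cost is SAP wording, a few programming lines and a slightly less favourable interruption rate.

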2.4.2 Prior concomitant and post therapies

Prior anti-neoplastic therapies

The number and percentage of patients who received any prior anti-neoplastic medications, prior anti-neoplastic radiotherapy or prior anti-neoplastic surgery will be summarized overall.

This summary will include medication: type of last therapy, setting at last therapy and best response to last medication. A separate listings will be produced for prior anti-neoplastic medications, radiotherapy, and surgery.

The above analyses will be performed using the FAS. Anti-neoplastic medications will be coded using the WHO Drug Dictionary (WHO-DD); anti-neoplastic surgery will be coded using MedDRA.

Post treatment anti-neoplastic therapy

Anti-neoplastic therapies since discontinuation of study treatment will be listed for the FAS in three separate listings: medications, radiotherapy, and surgery.

Concomitant therapy

Concomitant therapy is defined as all interventions (therapeutic treatments and procedures) other than the study treatment administered to a patient coinciding with the study treatment period. Concomitant therapy include medications (other than study drugs) starting on or after the start date of study treatment or medications starting prior to the start date of study treatment and continuing after the start date of study treatment.

Concomitant medications will be coded using the World Health Organization (WHO) Drug Reference Listing (DRL) dictionary that employs the WHO Anatomical Therapeutic Chemical (ATC) classification system and summarized by lowest ATC class and preferred term using frequency counts and percentages. Surgical and medical procedures will be coded using MedDRA and summarized by SOC and preferred term. Concomitant medications with immunosuppressive intent will be summarized by lowest ATC class and preferred term using frequency counts and percentages. Concomitant medications with immunosuppressive intent will be summarized by lowest ATC class and preferred term using frequency counts and percentages. These summaries will include:

1. Medications starting on or after the start of study treatment but no later than 30 days after start of last dose of study treatment and
2. Medications starting prior to start of study treatment and continuing after the start of study treatment.

Additional summaries will be provided to report medications starting between 31 days after last dose of study PDR001 and 150 days after last dose of PDR001. All reported concomitant therapies will be listed. Any concomitant therapies starting and ending prior to the start of PDR001 or starting more than 150 days after the last dose of PDR001 will be flagged in the listing. The safety set will be used for all concomitant medication tables and listing.

2.5 Analysis of the primary objective

The primary objective is to assess the clinical benefit of treatment with PDR001 + LAG525 at 24 weeks of treatment based on local investigator assessment.

2.5.1 Primary endpoint

The primary endpoint is the clinical benefit rate (CBR) (e.g. defined as CR, PR or SD) at week 24 by RECIST 1.1 for solid tumors and the Revised Response Criteria for Malignant Lymphoma, (Cheson et al 2007), for Lymphoma.

2.5.2 Statistical hypothesis, model, and method of analysis

The primary efficacy variable CBR is as defined below.

CBR at 24 weeks: CBR is defined as the proportion of patients with a best overall response of CR or PR or SD within the first 24 weeks of treatment.

In addition to tumor-specific measurements (e.g., radiological assessment of tumor response for solid tumors), progressive disease will also be considered when it was indicated either as a reason for the study treatment discontinuation or as a cause of on-treatment death. CR and PR (for solid tumors) require a confirmation that is at least a minimum of 4 weeks after the initial observation of response. Patients who had confirmed CR/PR or SD prior to or at 24 weeks, will be considered as achieving clinical benefit; patients who had confirmed CR/PR/SD prior to or at 24 weeks, but progressed at or after 24 weeks will also be considered as achieving clinical benefit.

CBR will be analyzed by comparing achieved CBR with a historical control rate of each tumor type, and if there is at least 80% probability that the response rate in a tumor type exceeds the historical rate, then the tumor type will be considered a success.

CBR will be analyzed, as mentioned below, by a Novartis designated vendor, [REDACTED].

The study will enroll patients from 7 tumor cohorts as mentioned in Section 1.1 study design.

We let Y_i be the response indicator for the i^{th} subject, and let R_g be the assumed probability of response within a control population and $\pi_g = \Pr(Y_i = 1 | g_i = g)$ be the underlying probability of response for group g within the trial. We transform to the logit scale for modeling purposes. Let θ_g be the mean log odds treatment effect, i.e.:

$$\theta_g = \log\left(\frac{\pi_g}{1 - \pi_g}\right) - \log\left(\frac{R_g}{1 - R_g}\right)$$

Thus, θ_g is the group specific logistic regression coefficient for group g . The primary analysis is a set of group specific tests that $\theta_g > 0$, meaning that the treatment is better than the assumed control rate for that group. Thus, we wish to test the set of hypotheses

$$H_{0g} : \theta_g \leq 0$$

$$H_{1g} : \theta_g > 0$$

We proceed in a Bayesian fashion, assigning a prior distribution (discussed below) and computing the posterior probability of H_{1g} within each group g . If, at the final analysis,

$$\Pr(\theta_g > 0 | \text{data}) > 0.80$$

then group g will be declared a success. Hence, the final analysis produces a separate decision for each group. The trial allows for early stopping of groups for futility, described below. No early stopping for success is allowed.

The statistical design borrows information across subgroups with a hierarchical model. The hierarchical model allows dynamic borrowing of information between groups such that more borrowing occurs when the groups are consistent and less borrowing occurs when the groups differ. In this way, the model is a compromise between the extremes of a completely pooled analysis as opposed to a separate analysis in each group. We additionally incorporate a clustering mechanism that allows borrowing within clusters but treats clusters separately. This minimizes borrowing across groups that are quite different in terms of CBR effects.

The hierarchical model approach involves two stages. The goal of both stages is to allow the data to drive the amount of borrowing across groups. If the data indicate a large amount of borrowing is appropriate (due to similar results), the model will borrow more and thus increase the overall power of the trial within each group. In contrast, if the data indicate a small amount of borrowing is appropriate (due to dissimilar results) the model will adjust and each group will stand more on its own. This “dynamic” borrowing property is distinct from other approaches which use a fixed informative prior or *apriori* assume an amount of borrowing across groups. Here the approach includes two stages to identify the appropriate amount of borrowing based on the data.

The first stage of model places the groups into distinct clusters. The purpose of this stage is to minimize borrowing of information across groups that appear to be quite different. Thus, for example, should 2 of the groups appear similar while the others differ significantly, the model may place a large probability on two clusters, one containing the two similar groups with the other containing the remaining groups. The model does not pick one particular clustering, but instead incorporates the uncertainty of the data in this determination, producing a probability distribution over the possible clustering. Thus, in our example, the model may consider it highly likely that the 2 similar groups are in one cluster with the remaining groups in another, but it would also retain lower probabilities on the possibility all groups are in one cluster (e.g. we are simply seeing differences in the two groups by chance) as well as other possibilities. The complete analysis averages over this uncertainty.

At the second stage, we place hierarchical models over the groups within each cluster (thus, conditional on the clustering, there is no borrowing of information across clusters, only within clusters). The hierarchical model assumes that the θ_g have an across groups distribution

$$\theta_g \sim N(\mu, \tau^2)$$

The across group mean μ and variance τ^2 are unknown, and hence have a prior distribution which is combined with the data to produce estimates of μ and τ^2 .

The variance component τ controls the degree of borrowing among groups. Small values of τ result in a greater degree of borrowing while large values of τ correspond to less borrowing. The parameter τ is estimated using the data, so the observed between group variation is a key component of the model behavior.

Combined, the two stages allow groups with similar results to borrow information between them (they will have a high probability of being in the same cluster) while groups with different

results with borrow far less information between them (they will have a low probability of being in the same cluster).

Details of the hierarchical model is provided in Appendix 4 of protocol.

Evaluation of trial success and futility

Interim monitoring will occur once 5 subjects have CBR data available within a cohort. Interim analyses will continue every 3 months thereafter provided at least 10 subjects contribute new CBR data to the subsequent interim. Simulation studies in this document approximate this interim plan, as they are timed 12 weeks apart without any restrictions on the number of new observations within the analysis.

At each interim analysis, the groups will be evaluated for early futility and sample size expansion by comparing posterior quantities for the CBR to pre-specified early stopping criteria.

Table 2-1 Historical CBR for each group

Group Index	Tumor Type	Median PFS (mo.)	Hist. CBR (%)	Hypothetical Yearly Average Accrual (Subjects)
1	SCLC	1.5	6.25	20
2	Gastroesophageal	5	43.50	16
3	STS	6.2	51.10	13
4	Prostate	4	35.40	11
5	Ovarian	3	25.00	10
6	Advanced NET	5	43.50	7
7	DLBCL	3	25.00	6

Early Futility

If there is less than 20% probability that the response rate in a subgroup exceeds the historical rate R_g , then the group will stop enrollment early for futility. Formally, enrollment will stop early for futility if:

$$\Pr(\pi_g > R_g) < 0.20.$$

A group is only eligible for early stopping once a minimum of 5 patients have been evaluated for response in that group.

Early Success

If there is at least 70% probability that the response rate in a subgroup exceeds the historical rate, then the subgroup will stop enrollment early for success. Formally, enrollment will stop early for success if:

$$\Pr(\pi_g > R_g) > 0.70.$$

A minimum of 5 subjects will need to be evaluated prior to declaring a group to be efficacious. This eligibility remains effective until the next interim analysis is conducted, at which point eligibility is re-evaluated based on the currently available data and corresponding model outcomes.

Post-Expansion Futility

If there is less than a 60% probability that the clinical benefit rate in a group exceeds the historical rate, then the group will stop enrollment early for futility. Formally, enrollment will stop early for futility if:

$$\Pr(\pi_g > R_g) < 0.60.$$

A group is only eligible for this post-expansion stopping criterion once the group has expanded to a sample size beyond 10 subjects enrolled. Note this post-expansion futility is a stricter futility rule than that used prior to sample size expansion.

Final Analysis

The final analysis will occur when both accrual and follow-up are complete for all groups. If, at the completion of the trial, there is at least 80% probability that the response rate in a group exceeds the historical rate, then the group will be considered a success. Formally:

$$\Pr(\pi_g > R_g) > 0.80.$$

In addition of above mentioned Bayesian analyses with all solid tumor types combined and separately for each hematological tumor type, the CBR estimate will be provided with its 95% exact CI. For tumor types (within the solid tumors) that have ten (10) or more patients, separate summaries will be performed by the tumor type and will also be displayed graphically. In the event that there are fewer than 4 patients for a hematological tumor type, only listing will be provided for that tumor type. In addition to summary by tumor types, separate summaries will also be provided by prior line of therapy and number of treatment cycles received.

CBR estimate with its 95% exact CI will also be provided for CBR by end of study using full analysis set. Additionally, for tumor cohort Prostate cancer an association of response(CBR) with PSA(prostate specific antigen) will be explored by summarizing the response at different level of PSA stratified by quartiles at baseline and 24 week.Similar analysis will also be repeated for ovarian cancer with Cancer Antigen-125 (CA-125).

